7.1 Effectiveness Measures

7.1.1 Primary Effectiveness Measure

[figure not shown]
The primary effectiveness measure is the EI's photo assessment of chin retrusion using the ACRS described in Table 6 and Figure 1. The EI will assess 2D profile images of the left side of the chin rendered by the Canfield image analysis technician from the 3D images.

Table 6 Allergan Chin Retrusion Scale

Score	Grade	Description
0	None	No chin retrusion; Chin midpoint* at or in front of the lower vermillion border vertical line
1	Minimal	Minimal chin retrusion; Chin midpoint* is between the labiomental sulcus vertical line and lower vermillion border vertical line
2	Moderate	Moderate chin retrusion; Chin midpoint* at labiomental sulcus vertical line
3	Severe	Severe chin retrusion; Chin midpoint* slightly behind labiomental sulcus vertical line
4	Extreme	Extreme chin retrusion; Chin midpoint* significantly behind labiomental sulcus vertical line

* Chin midpoint: the midpoint between the labiomental sulcus and the inferior point of the chin

Figure 1 Lines Used in the ACRS Descriptors

[figure not shown]
The ACRS is a 5-point ordinal scale developed by Allergan to grade the severity of chin retrusion. The ACRS contains photographic images of subjects representing different Fitzpatrick skin types, race categories, and severities of chin retrusion (0 = None, 1 = Mild, 2 = Moderate, 3 = Severe, 4 = Extreme). A scale validation study was conducted to assess the inter- and intra-rater reliability of the ACRS. The results confirmed that the ACRS is validated and appropriate to be used as a primary effectiveness measure for this study.

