8.5 Sample Size Calculation

A sample size of 120 subjects in the treatment group and 40 subjects in the control group will provide > 99% power to detect a difference of at least 40% in the responder rates between the groups. This calculation is based on a 2-sided Fisher's exact test at the 5% level. The treatment group is assumed to have at least 80% responder rate and the control group will have at most 40% responder rate. Assuming a screen fail rate of 15% and a drop-out rate of 15% between randomization and the month 6 visit, up to 224 subjects will be enrolled, resulting in up to 168 subjects randomized to the treatment group and up to 56 subjects to the control group (3:1 ratio). Assuming a screen fail rate of 15% and an overall drop-out rate of 20% between randomization and study completion, an estimated 152 subjects will complete the study.

With up to 168 subjects randomized to the treatment group and an estimated screen fail rate of 15%, it is estimated that at least 143 subjects will be treated in the study. With 143 treated subjects, there is at least an 88% power to detect an AE related to treatment with an incidence rate of 1.5% in the population using a 1-sided exact binomial test at the 2.5% level.

Due to an estimated 15% of subjects having a baseline photo assessment of 1 or 4, up to 36 additional subjects may be randomized to ensure sufficient power for sensitivity analyses, resulting in a total of up to 260 subjects enrolled.

The commercial software, PASS (2008, Version 8.0.13), was used for the power calculation. The sample size calculation used an inequality test for 2 proportions to demonstrate that the treatment group is superior to the control group. The safety calculation used an inequality test for 1 proportion.

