5.1.1.3 Statistical Methodology

The methodologies defined below apply as specified to individual endpoints defined in this SAP.

Table 5-2 Statistical Methodology

Methodology	Description
Categorical counts	
 Number and percent of subjects in individual categories 
 Subjects with ≥ 1 qualifying event counted once per individual category N included = participants with non-missing value for by visit analysis
Event descriptives	
 Number and percentage of events in individual categories 
 Events counted individually for each instance Percentage denominator = total number of events
Continuous descriptives	
 N included, mean, standard deviation (SD), median, minimum, maximum N included = subjects with non-missing value
CFB descriptives	
 Continuous descriptives for baseline, postbaseline, and change from baseline (CFB) values N included = subjects with non-missing values at both baseline and the specified postbaseline analysis visit
CFB Paired T	
 Continuous descriptives for baseline, postbaseline, and CFB values 
 P-values from a 2-sided paired t-test comparing baseline and postbaseline values N included = subjects with non-missing values at both baseline and the specified postbaseline analysis visit
Responder	
 Categorical descriptives for responders and nonresponders 
 Include count and percent along with exact binomial 95% CI P-values from 2-sided Fisher's exact test N included = with non-missing values at both baseline and the specified postbaseline analysis visit

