5.1.1.4 Missing Data

General missing data handling conventions are specified and summarized as follows:

Table 5-3 Missing Data Handling by Endpoint Type

Endpoint type	Timing	Missing Data Handling
Responder	Month 6 (no-treatment control period)	
 All subjects included (ITT population) Multiple imputation with 5 imputed datasets is applied to subjects with no postbaseline values using the below model: $\text{Month 6 ACRS} = \beta_0 + \beta_1 \text{Baseline ACRS} + \beta_2 \text{Month 1 ACRS} + \beta_3 \text{Month 3 ACRS}$ 
where ACRS score is based on photo assessment.

Responder	Month 6 (no-treatment control period)	
 All subject included (ITT population) Last observation carried forward (LOCF) for subjects with no postbaseline values

The above missing data handling conventions will only be used for sensitivity analysis of the primary effectiveness endpoint.

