5.1.3.1 Primary Effectiveness Endpoint

The primary effectiveness endpoint will be met if the responder rate at month 6 for the treatment group is statistically greater than that for the control group at month 6 and the observed responder rate at month 6 for the treatment group is greater than 50%. A responder is a subject who shows clinically significant improvement, i.e., ≥ 1 -point decrease, on the ACRS from baseline based on EI assessment of 2D renderings of the chin profile.

The primary effectiveness analysis is summarized in Table 5-15.

Table 5-15 Primary Effectiveness Analyses

Endpoint	Description	Timing	Methodology
Primary: Responder analysis based on photo ACRS	
• Superiority of the treatment group over no-treatment control group• Responder rate of treatment group is greater than 50%	Month 6	Responder

The primary effectiveness analysis will be performed on the mITT population without any missing data imputation. Sensitivity analysis will be performed using ITT and PP populations as well as using missing data handling conventions as described in Section 5.1.1.1.4. Additionally, sensitivity analysis will be performed on mITT subjects with a baseline ACRS photo score of 2 or 3.

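### The multiple-imputation model in SAP Table 5-3 treats the whole-grade ACRS as a linear outcome with no treatment term and no rule for turning an imputed score into responder status, so the treatment responder rate among imputed subjects comes out too low

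*SAP*

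**What the plan says.** - **Scale.** Protocol section 7.1.1: "The ACRS is a 5-point ordinal scale developed by Allergan to grade the severity of chin retrusion". The grades are whole numbers from 0 to 4.
- **Response.** SAP section 5.1.3.1 defines a responder by a decrease of 1 point or more "on the ACRS from baseline based on EI assessment of 2D renderings of the chin profile".
- **Imputation.** SAP section 5.1.1.4, Table 5-3, under the Responder endpoint: "Multiple imputation with 5 imputed datasets is applied to subjects with no postbaseline values using the below model". The model sets month 6 photo ACRS equal to an intercept plus a coefficient each for baseline, month 1 and month 3 ACRS. It shows no treatment term, and nothing says that it is fitted by arm. The table does not name the imputation method, give a rounding rule, or say how an imputed score becomes responder status.
- **Analysis of responders.** SAP section 5.1.1.3, Table 5-2, gives counts, percentages, an exact confidence interval and "P-values from 2-sided Fisher's exact test". No rule for combining the five datasets appears.
- **Role.** The SAP limits these conventions to sensitivity analysis of the primary endpoint. The primary analysis is on mITT without imputation (section 5.1.3.1).

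**The concern.** Two features of the equation matter, and they act separately.

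**The scale.** An observed subject can change only by whole grades, so a fall of 1 or more is the same event as a fall of more than 0.5 on a continuous scale. A draw from a linear model is fractional. From a baseline of 2, a draw of 1.2 is a fall of 0.8. Cut at 1.0 it is a non-response, although the nearest real grade, 1, would be a response.

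**The arm.** Subjects with no postbaseline value also lack month 1 and month 3 scores, so only their baseline grade informs the prediction. Without a treatment term, a treated subject and a control with the same baseline receive the same predicted distribution.

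This analysis is meant to show whether missing data could alter the primary result. If the method itself moves the imputed rates by tens of points, the analysis no longer answers that question. Two programmers following Table 5-3 could also obtain clearly different answers.

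**Working it through.** **1. The plan's own figure.** Protocol section 8.5 states: "A sample size of 120 subjects in the treatment group and 40 subjects in the control group will provide > 99% power". The rates are given as "The treatment group is assumed to have at least 80% responder rate and the control group will have at most 40% responder rate", and "This calculation is based on a 2-sided Fisher's exact test at the 5% level". Exact enumeration of Fisher's test with 120 vs 40 subjects at 80% vs 40% gives 99.5%, so the stated power reproduces.

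**2. Numbers for the check.** The protocol writes: "Assuming a screen fail rate of 15% and a drop-out rate of 15% between randomization and the month 6 visit". With up to 168 and 56 subjects, 168 × 0.85 = 142.8 and 56 × 0.85 = 47.6, hence 143 and 48. All of the 15% drop-outs are taken to have no postbaseline value.

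**3. Assumptions not in the documents.** Baseline grades 1/2/3/4 at 10/45/40/5% (the protocol gives only 15% for grades 1 and 4 together). Missingness is completely at random. There are three distributions of improvement in grades, each with true response of 80% and 40%:

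| | Treatment | Control |
|---|---|---|
| A | -1: 2%, 0: 18%, 1: 55%, 2: 25% | -1: 10%, 0: 50%, 1: 40% |
| B | 0: 20%, 1: 40%, 2: 30%, 3: 10% | -1: 15%, 0: 45%, 1: 30%, 2: 10% |
| C | 0: 20%, 1: 80% | 0: 60%, 1: 40% |

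**4. Hand check, distribution A.** P(improvement ≥ c) = 1 − Φ((c − mean)/SD).
- Treatment: mean −0.02 + 0.55 + 0.50 = 1.03; SD = √(1.57 − 1.03²) = 0.71. P(≥ 1) = 52%; P(≥ 0.5) = 77%. Truth 80%.
- Control: mean 0.30; SD = √(0.50 − 0.09) = 0.64. P(≥ 1) = 14%; P(≥ 0.5) = 38%. Truth 40%.
- Arms pooled 3:1: mean 0.75 × 1.03 + 0.25 × 0.30 = 0.85; SD = √(1.3025 − 0.8475²) = 0.76. P(≥ 1) = 42%; P(≥ 0.5) = 67%, the same in both arms.

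**5. Simulation.** 1,500 trials per distribution, five proper normal-regression imputations from baseline. Responder rate among imputed subjects, treatment / control (truth 80 / 40):

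| Variant | A | B | C |
|---|---|---|---|
| Pooled, unrounded (literal reading) | 41 / 41 | 50 / 50 | 26 / 26 |
| By arm, unrounded | 50 / 15 | 60 / 23 | 31 / 13 |
| Pooled, rounded | 67 / 67 | 71 / 71 | 67 / 66 |
| By arm, rounded | 76 / 39 | 81 / 43 | 77 / 42 |

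A separate simulation gave 35-51% in both arms (pooled, unrounded), 44-60% and 13-23% (arm term, unrounded), 66-73% in both arms (pooled, rounded), and 76-82% and 38-47% (arm term, rounded). The ranges quoted in this point span both runs.

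**6. Whole-arm effect.** Arm rate = 0.85 × true rate + 0.15 × imputed rate.
- Pooled, unrounded, A: treatment 68 + 0.15 × 40.9 = 74.1%; control 34 + 0.15 × 41.0 = 40.2%. Over A to C: 72-75% and 38-41%.
- By arm, unrounded: 73-77% and 36-37%; difference 37-40 points.
- Pooled, rounded: 78-79% and 44-45%.
- Either pooled variant: the difference is about 0.85 × 40 = 34 points, because the imputed subjects contribute almost none.

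Approximate power of the two-arm comparison stays at 98.9% or more in every variant.

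**The case against.** The strongest reply is that Table 5-3 lists predictors and does not name a method. Predictive mean matching could use this same linear predictor and return only observed whole grades, and a programmer might round. That is correct: unrounded scoring is the literal reading, not a stated rule. The reply does not clear the model, though. Rounding without a treatment term places imputed controls 26 to 31 points too high in distributions A to C, and matching on a predictor without treatment would also ignore the arm. The SAP has to settle both matters.

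Three stronger readings are tempting, and the documents do not support them.
- *A reader might infer that imputed rates are low in both arms.* That needs a treatment term or by-arm fitting, which the SAP does not contain. With the model pooled, only the treatment arm is reliably low.
- *A reader might infer a threat to the 50% criterion, or that the primary result would look fragile.* The imputation does not enter the primary analysis, and the whole-arm treatment rate stays at about 72% or higher in the tabulated runs.
- *A reader might infer that the Fisher p-value makes pooling impossible.* Table 5-2 also yields proportions, which have standard errors. The combining rule is unstated; an error is not shown.

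It also stands that Table 5-3 covers only subjects with no postbaseline value. Those lost after a month 1 or month 3 assessment may not be imputed at all, so the 15% overstates the number affected.

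**Conclusion.** The point holds as a defect in one sensitivity analysis. On the literal reading, imputed treated subjects are credited with response about 30 to 54 points too rarely (26-51% against 80%), while the error for controls can go either way. Neither obvious partial repair is enough: a treatment term alone leaves the scale problem, and rounding alone leaves the arm problem. With up to 15% imputed, the between-arm difference shrinks from 40 to about 34 points when the arms are pooled. The trial's success conclusion does not change under the plan's own rates.

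The direction for the treatment arm was the same under every set of assumptions tried. The exact figures depend on the assumed change distributions, baseline mix and random missingness. The change should be made, but it is not critical to the primary claim.

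**What to change.** In SAP Table 5-3, before database lock:
1. Impute month 6 ACRS on its grade scale, by proportional-odds logistic imputation or by predictive mean matching restricted to grades 0-4.
2. Put treatment in the imputation model, or fit the model separately by arm.
3. State that responder status is derived from the imputed whole grade.
4. State the combining rule: estimate the risk difference and its standard error in each imputed dataset, and pool by Rubin's rules.

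Items 1 and 2 are needed together. The cost is a few lines of SAP text and a different option in the imputation procedure. No new data and no change to the primary analysis are required.

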5.1.1.5 Site Pooling

The impact of investigational sites on the primary effectiveness analysis at Month 6 will be evaluated by including investigational site, treatment assignment, and their interaction as

predictor variables in a multivariate logistic regression analysis with response status on the ACRS as the dependent variable. Investigational sites with few enrolled subjects may be pooled with other sites based on subjects enrolled, geographical region, or other site characteristics. The interaction between site and treatment will be considered significant if the p-value of this interaction is less than 0.05.

5.1.2 Demographics

5.1.2.1 Analysis Populations

The distribution of subjects within the analysis populations will be summarized as follows:

Table 5-4 Analysis Population Summaries

Endpoint	Description	Timing	Methodology
All Consented	Distribution of all randomized, Randomized but Discontinued Before Treatment, Not Randomized (with Reason for Randomization Failure)	Screening period	Listing
Not Randomized	List of not randomized subjects with randomization failure reasons	Screening period	Listing
ITT, mITT, PP and Safety populations	Distribution in total and by treatment group	After randomization	Categorical counts

5.1.2.2 Subject Disposition

Subject disposition encompasses the distribution of subjects who enter, complete, and discontinue during each specified analysis period (i.e., screening and treatment periods), along with eCRF-reported discontinuation reasons from each respective analysis period. A subject in the treatment group is considered a completer if s/he completes the month 12 visit without receiving repeat treatment or completes the month 1 visit after receiving repeat treatment. A subject in the control group is considered a completer if s/he completes the month 6 visit without receiving optional treatment or completes the month 6 visit after receiving optional treatment. Subject disposition will be summarized as follows:

Table 5-5 Subject Disposition Summaries

Endpoint	Description	Timing	Methodology
Study disposition	Distribution in the randomized subjects in total and by treatment group	Month 6 and final	Categorical counts

5.1.2.3 Protocol Deviations

Protocol deviations will be defined in a separate document, including importance classification. Protocol deviations will be summarized as follows:

Table 5-6 **Protocol Deviation Summary**

Endpoint	Description	Timing	Methodology
Important protocol deviations	Important protocol deviation will be listed	—	Categorical counts/Listing

5.1.2.4 Demographics

Demographics will be summarized for mITT population in total and by treatment group as follows:

Table 5-7 **Demographic Summaries**

Endpoint	Description	Timing	Methodology
Age	Age (years) relative to informed consent date	Informed consent	Continuous descriptives
Sex, race, and ethnicity	
○ Sex
○ Female○ Male○ Race
○ White○ Black or African American○ Asian○ American Indian or Alaska Native○ Native Hawaiian or Other Pacific Islander● Ethnicity
○ Hispanic or Latino○ Not Hispanic or Latino	Screening Period	Categorical counts

5.1.2.5 Baseline Characteristics

Baseline characteristics will be summarized in total and by treatment group for the mITT population as follows:

Table 5-8 Baseline Characteristics Summaries

Endpoint	Timing	Methodology

• Sun exposure (hours per day)• Duration of Smoking	Latest assessment prior to randomization	Continuous descriptives

• Fitzpatrick Skin Phototype
◦ I, II, III, IV, V, VI• Smoking history	Latest assessment prior to randomization	Categorical counts

5.1.2.6 Medical History

Medical history, encompassing abnormalities, surgeries, and cosmetic procedures reported as occurring before the Screening Visit, will be coded using the Medical Dictionary for Regulatory Activities (MedDRA), version 18.1 or newer. Unique subjects who report medical history events will be presented as subject listing for the Safety Population.

Table 5-9 Medical History

Endpoint	Timing	Methodology
Abnormalities and surgeries occurring before the Screening Visit	Screening Period	Listing

5.1.2.7 Prior and Concomitant Medications

Medications will be coded using the World Health Organization (WHO) Drug Dictionary, version March 2014 or newer. Unique subjects who reported medications (Anatomical Therapeutic Chemical (ATC) 4 class and PT) will be presented as subject listing for the Safety Population.

Table 5-10 Medication

Endpoint	Description	Timing	Methodology
Prior medications	Medications taken before the study treatment start date and time for the treatment group and before randomization date and time for the control group, regardless of medication end date	Screening Period prior to treatment/randomization	Listing
Concomitant medications during control period	Medications taken on or after the study treatment start date and time for the treatment group and after randomization date and time but before optional treatment date time (at month 6) for the control	Control Period	Listing

Endpoint	Description	Timing	Methodology
Concomitant medications during treatment period	group, regardless of medication end date Medications taken on or after the study treatment start date and time for both control and treatment groups, regardless of medication start date	Treatment Period	Listing

5.1.2.8 Exposure to Study Treatment

Treatment exposure related variable will be summarized for safety population by treatment group as follows:

Table 5-11 **Exposure to Study Treatment**

Endpoint	Description	Timing	Methodology
Volume injected	Initial, Touch-up, Combined initial and touch-up, Repeat	Treatment period	Continuous descriptives

5.1.2.9 Administration of Study Treatment

Variables related to administration of treatment will be summarized for safety population by treatment group as follows:

Table 5-12 **Administration of Study Treatment**

Endpoint	Description	Timing	Methodology

• Pretreatment Anesthesia type• Planes of injection• Injection technique• Needle/cannula used• Injection ease• Product moldability	Initial, Touch-up, Repeat (Repeat for Treatment Group only)	Treatment period	Categorical counts
Pretreatment Anesthesia duration	Initial, Touch-up, Repeat (Repeat for Treatment Group only)	Treatment period	Continuous descriptives

5.1.3 Effectiveness Analyses

Effectiveness analyses will be based on the mITT Population.

The following effectiveness assessments are defined:

Table 5-13 Effectiveness Assessments

Assessment	Description
Chin retraction based on photo assessment	Assessed by EI using the 5-point ACRS (see Appendix A). The EI will assess 2D profile images of the left side of the chin rendered by the Canfield image analysis technician from the 3D images.
Chin retraction based on live assessment	EI's live ACRS assessment
Global Aesthetic Improvement Scale (GAIS)	Assessments by subject and EI based on 5-point GAIS (see Appendix B)
Satisfaction with Chin module	Assessed by subject response on the Satisfaction with Chin module of the validated FACE-Q questionnaire (see Appendix C)

Baseline assessments for applicable effectiveness endpoints are defined as follows:

Table 5-2 Effectiveness Endpoint Baseline Definitions

Endpoint	Description	Timing
• Chin retraction based on photo assessment	Baseline refers to the photo evaluation by EI at randomization (or screening if no usable assessment is available at randomization)	Randomization/ Screening
• Chin retraction based on live assessment	Baseline refers to the joint live evaluation by EI and TI at randomization (or screening if no usable assessment is available at randomization)	Randomization/ Screening
• Satisfaction with Chin module	Baseline refers to the evaluation at screening	Screening

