8.2 Collection/Derivation of Primary and Secondary Effectiveness Assessments

8.2.1 Primary Effectiveness Variable

The primary effectiveness variable is defined as the change in the EI's assessment of chin retrusion using the ACRS based on 2D renderings of 3D images. A subject showing \geq 1-point improvement (decrease in retrusion) in ACRS score compared with baseline will be considered to be a responder. The primary evaluation timepoint is month 6 after last treatment for subjects in the treatment group and month 6 after randomization for subjects in the control group.

The primary effectiveness endpoint is the difference in mean scores on the ACRS between the treatment group and the control group at month 6.

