10.1 Subject Entry Procedures

10.1.1 Overview of Entry Procedures

Prospective subjects as defined by the criteria in Sections 5.3 and 5.4 (inclusion/exclusion criteria) will be considered for entry into this study. A subject is considered to have entered the study upon signing the ICF, which will occur prior to any screening procedures.

Screening procedures include:

- collection of demographic information
- collection of height, weight, and vital signs
- evaluation of Fitzpatrick skin phototype and history of sun exposure
- collection of smoking history
- collection of medical/surgical/cosmetic/dental procedures history
- administration of urine pregnancy test to female subjects of childbearing potential (women who are not of childbearing potential are considered as postmenopausal for at least 1 year or have no uterus)
- capture of 3D facial digital images
- evaluation by both the EI and the TI of the subject's chin retrusion using the ACRS

- evaluation of inclusion/exclusion criteria
- administration of FACE-Q questionnaire modules for Satisfaction with Chin and Psychological Well-Being
- EI assessments of subject's facial sensation and facial function
- collection of AEs, concomitant medications, and concurrent procedures

Subjects choosing not to participate in facial digital imaging through checkbox selection on the ICF will be excluded from the study. Allergan shall have full ownership rights to any facial digital imaging derived from the study.

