12.4 Documentation

12.4.1 Source Documents

Source documents may include a subject's medical records, hospital charts, laboratory notes, device accountability records, TI and EI assessments of chin retrusion, [REDACTED]
[REDACTED] subject FACE-Q questionnaires, [REDACTED]
[REDACTED]

diaries, EI and subject assessments of global aesthetic improvement in the chin area using the GAIS, photographic negatives, digital images, or renderings, clinic charts, the TI's subject study files, results of pregnancy tests, and any other diagnostic tests that may be performed, such as X-rays, laboratory tests, and magnetic resonance imaging. If the Serious Adverse Event Form and Pregnancy Surveillance Form are used in this study, they are also considered source documents. The TI's copies of the eCRFs serve as part of the TI's record of a subject's study-related data.

The following information is to be entered into the subject's medical record:

- Subject's name

- Subject's contact information
- Date that the subject entered the study, subject number, and subject randomization number
- Study title and/or the protocol number and study Sponsor
- A statement that IC was obtained, including the date and a statement that HIPAA Authorization or other country and local subject privacy required documentation for this study has been obtained, including the date
- Details of the injection procedure including anesthetic used, treatment areas injected, volume injected in each treatment area, ease of injection, details regarding molding and massage, kit and lot numbers of study device injected, subject's assessment of procedural pain
- Dates of all subject visits
- All concurrent medications (List all prescription and non-prescription medications being taken at the time of enrollment. At each subsequent visit, changes to the list of medications are to be recorded.)
- Occurrence and status of any AEs
- Date the subject exited the study, and a notation as to whether the subject completed the study or reason for discontinuation
- Results of laboratory tests performed by the site (eg, results of urine pregnancy tests)

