	
• [REDACTED]• [REDACTED]• Section 7.1.1 - clarified primary effectiveness measure as the EI assessment of 2D profile images of the left side of the chin rendered from the 3D images by the Canfield image analysis technician• Section 8 - clarified baseline as EI assessment of the photo taken at randomization (or screening if the randomization image is not usable)• Section 8.2.1 - clarified the primary effectiveness variable as EI's assessment of chin retrusion using the ACRS based on ACRS based on 2D renderings of 3D images• Section 8.3.2 (second bullet) - the timepoint for secondary effectiveness analysis was corrected from "month 3" to "month 6"• Section 8.5.1 - corrected to Section 4.4.2• [REDACTED]• Section 13.1 - removed study report reference• Section 13.2 - subheading deleted
24 May 2016/2	
• [REDACTED]• Synopsis (Sample Size Calculation) - added "Assuming a drop-out rate of 20% between randomization and study completion, an estimated 170 subjects will complete the study."• Section 8.5 - added "Assuming a drop out-rate of 20% between randomization and study completion, an estimated 170 subjects will complete the study."• [REDACTED]
11 Jan 2017/3	
• Synopsis (Number of Subjects) - Changed "212" to "224"• Synopsis (Study Design) - Treatment Group: Added "At the month 6 visit, the EI will conduct a live ACRS assessment."• Synopsis (Study Design) - Control Group: Added "At the month 6 visit, the EI will conduct a live ACRS assessment."• Synopsis (Inclusion criteria) - Criterion #2: Added the category "Extreme" to chin retrusion and grade "4" on the ACRS• Synopsis (Response Measures) - Effectiveness: Primary effectiveness measure added "photo" in front of "assessment of chin retrusion"• [REDACTED]• Synopsis (Statistical Methods) - Sample Size Calculation: Changed screen fail rate from "10%" to "15%", number of subjects from "212" to "224", number of subjects per treatment group from "159" to "168", number of subjects in the control group from "53" to "56", changed the number of

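### Live ACRS change compares a joint EI-and-TI baseline grade with an EI-only follow-up grade, which can create or hide a one-grade change in this non-primary measure

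*SAP*

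**What the plan says.** SAP 5.1.3 contains both halves of the mismatch. Table 5-13 describes the live measure as "EI's live ACRS assessment", with no mention of the TI. The baseline table that follows (Table 5-14 in the list of tables) gives the live baseline as "Baseline refers to the joint live evaluation by EI and TI at randomization", falling back to screening if nothing usable exists at randomization. The photo row of the same table names the EI alone: "Baseline refers to the photo evaluation by EI at randomization".

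For follow-up, the Amendment 3 entry in Protocol Section 14 records text added for both groups: "At the month 6 visit, the EI will conduct a live ACRS assessment". The same entry adds the EI's live ACRS to the effectiveness analyses. A log entry is only supporting evidence, because the current design text is largely redacted, but it agrees with Table 5-13.

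On what was recorded at baseline, Protocol 10.1.1 lists among screening procedures "evaluation by both the EI and the TI of the subject's chin retrusion using the ACRS", and Protocol 12.4.1 lists "TI and EI assessments of chin retrusion" among source documents. No visible text says how two ratings become one joint grade.

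**The concern.** A change score is easiest to read when the same rater, working in the same way, supplies both ends. The SAP does this for photo ACRS but not for live ACRS. If the joint grade at baseline is one step above the EI's own view, and the EI repeats that view at month 6, the record shows a one-grade improvement in an unchanged chin. If the joint grade is one step below, a true one-grade improvement disappears. On a five-grade scale, where one grade defines response for the photo measure, a single step decides the classification.

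Protocol 4.3.3 requires prior assessments, including scores, to be kept from the EI, so the EI is not expected to anchor on the joint grade at month 6.

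At stake is the reading of live ACRS, which is the only visible second reading of the primary scale by another modality. It may agree or disagree with the photo result partly because of how the baseline was graded.

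**Working it through.** **1. The plan's own figure.** Protocol 8.5 and SAP 5.2 state power above 99% for 120 versus 40 subjects at 80% versus 40% response (2-sided Fisher's exact test, 5%). Exact enumeration gives 99.5%, and the normal approximation gives 99.7%. The figure reproduces. It concerns photo ACRS and does not depend on the live baseline.

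**2. Who rates what.**

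| Measure | Baseline | Month 6 |
|---|---|---|
| Photo ACRS (primary) | EI | EI |
| Live ACRS | EI and TI jointly | EI |

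**3. Size under stated assumptions.** The documents give no EI-TI agreement rate, so every input here is assumed:
- D = share of subjects in whom EI and TI differ by one grade: 20-30%
- L = share of those in whom the EI is the lower rater: 1/2
- H = share of those in whom the joint grade is the higher one: 1/4 to 1/2
- the EI repeats his or her own grade at month 6 when nothing has changed

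False improvement among subjects with no true change = D × L × H.
- Low end: 0.20 × 0.5 × 0.25 = 2.5%
- High end: 0.30 × 0.5 × 0.5 = 7.5%

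If the EI is the higher rater in the other half, and the joint grade is the lower one equally often, the same 2.5-7.5% have a baseline one step too low. A true improvement of exactly one grade is then hidden.

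**4. Within arm versus between arms.** Borrow the plan's photo rates (80% and 40%) as an assumption for live ACRS, and let d be the share shifted in either direction. Only non-responders can become false responders:
- d = 2.5%: 0.80 + 0.20 × 0.025 = 80.5%; 0.40 + 0.60 × 0.025 = 41.5%; difference 39 points
- d = 7.5%: 0.80 + 0.20 × 0.075 = 81.5%; 0.40 + 0.60 × 0.075 = 44.5%; difference 37 points

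If every true responder improved by exactly one grade and the mirror effect also applies, the difference becomes 40 × (1 − 2d). That is 38 points at d = 2.5% and 34 points at d = 7.5%. When both arms are rated alike, the between-arm difference shrinks somewhat and is not inflated. A single-arm rate can move either way.

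**5. Illustration with rating error.** A simulation of 400,000 subjects per scenario assumed no true change, latent severity normal (mean 2.5, SD 0.6), scores rounded to 0-4, and baselines of 2 or 3 kept.

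| Baseline | False improvement / false worsening, error SD 0.3 | Same, error SD 0.5 |
|---|---|---|
| EI only | 15.5% / 15.5% | 23.7% / 23.7% |
| Joint, lower of the two | 8.4% / 22.5% | 14.5% / 32.8% |
| Joint, higher of the two | 22.4% / 8.4% | 33.0% / 14.3% |

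The joint rows assume no systematic TI-EI difference. With a TI-minus-EI shift from −0.25 to +0.5 grades, false improvement ranges over about 5-44% (SD 0.3) and 11-46% (SD 0.5), depending on the combining rule. The exact balance in the EI-only row owes something to the assumed mean lying midway between grades 2 and 3. The total error hardly changes (for example 15.5 + 15.5 = 31.0% versus 22.4 + 8.4 = 30.8%). The joint baseline mainly makes it lopsided, in a direction set by an unstated rule.

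**The case against.** The strongest reply is that little visible in the plan depends on this. Live ACRS is neither the primary endpoint ("Primary: Responder analysis based on photo ACRS") nor one of the three secondary endpoints. Its own responder rule and analysis are not visible, because the other-effectiveness text and the Table 5-17 entry are redacted. That live change is analysed is inferred from its having a defined baseline and from the Amendment 3 log. A joint grade may also be a sensible baseline: in the simulation some combining rules give less false improvement than an EI-only baseline, and the EI-only baseline still leaves 15.5-23.7%. Finally, the two places that suggest separate scores do not prove that the EI's live score at randomization was recorded on its own. All of this stands, and it keeps the point small. It does not remove the mismatch inside SAP 5.1.3.

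A reader might infer more than the documents support:
- **A full change of rater.** The EI takes part at both times. The change is from a two-person to a one-person rating.
- **Loss of the only check on the primary.** EI and subject GAIS and the FACE-Q chin module are secondary measures. The primary also has ITT, PP, multiple-imputation, LOCF and baseline-2-or-3 sensitivity analyses. No visible text gives live ACRS the role of checking the primary.
- **False response in 5-15% of each arm.** Under the assumptions in the working, the range is 2.5-7.5% and applies only to subjects with no true change.
- **Bias favouring the device.** The direction depends on an unstated combining rule and on any EI-TI severity difference. Protocol 4.3.3 leaves the TI unblinded, but the documents do not say whether the joint rating comes before the assignment is known, so a one-arm shift cannot be asserted.

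**Conclusion.** The mismatch is in the SAP as written: live ACRS is the EI's measure, but its baseline is a joint EI-and-TI grade. It can create or hide a one-grade change with no change in the chin.

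The reach is limited to the live ACRS analysis, and mainly to within-arm live rates. The primary comparison, its power and the secondary endpoints are untouched.

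The size cannot be derived from the documents. Under the assumed disagreement (20-30% of subjects, EI lower in half, joint grade the higher in a quarter to a half of those), about 2.5-7.5% of subjects with no true change would show false improvement, with a mirror effect hiding response. This is a minor point, worth correcting because an avoidable lopsided error can be removed cheaply.

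**What to change.** In the live ACRS row of the SAP 5.1.3 baseline table:
- Define baseline as the EI's own live score at randomization, or at screening if that is not usable, wherever it was recorded separately.
- Keep the joint score for a sensitivity analysis, and state how it was formed.
- Where only a joint score exists, flag those subjects and report the live result with and without them.
- If no separate EI scores exist at all, say that live change compares a joint with a single rating, and interpret it only as a between-arm comparison.

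The SAP should also state whether the joint rating was made before the TI knew the assignment.

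The cost is one table row, a flag and one extra run of the live analysis. The SAP is due for approval before database lock, so the change belongs there. The downside is that some subjects may lack a separate EI baseline, so the main live analysis could mix baseline types. The flag and the with-and-without report make that visible.
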